COMORBIDITIES	INCLUDED	EXCLUDED		EXCLUDED
SUICIDALITY	ASSESSED	NOT ASSESSED		NOT ASSESSED
HEALTH ECONOMICS	ASSESSED	NOT ASSESSED		NOT ASSESSED
AMOUNT OF TREATMENT	20-30 SESSIONS	15-30 SESSIONS		20 SESSIONS
PRIMARY ASSESSMENT FOR REMISSION	AT END OF TREATMENT PHASE	AT END OF TREATMENT PHASE		AFTER 4 WEEKS OF TREATMENT

II. STUDY OBJECTIVES

A. Primary Objective

To assess the efficacy of rTMS in veterans to bring about remission of TRMD.

B. Secondary Objectives

1. To evaluate the durability of benefit of rTMS in treatment of TRMD (patients receiving rTMS are more likely to remain in remission at 24 weeks post treatment than those receiving sham).

2. To evaluate the efficacy of rTMS in bringing about a significant decrease in depressive symptoms (a $\geq 50\%$ decrease in the Hamilton Rating Scale for Depression).
3. To determine whether depressive symptoms, suicidality, PTSD, substance abuse, cognitive function and quality of life improve with rTMS treatment.
4. To determine whether age, severity of symptoms at baseline, comorbidity with substance abuse or PTSD, duration of illness, and prior treatment resistance, predict differential treatment response.
5. To evaluate the cost effectiveness of rTMS in the treatment of depression in the VA Healthcare System.

III. OUTCOME MEASURES

A. Primary Outcome Measures

The proportion of participants achieving remission from depression based on the Hamilton Rating Scale for Depression of ≤ 10 at the end of the acute treatment phase.

B. Secondary Outcome Measures

The selection of secondary outcome measures is based on their use in previous studies in major depression, where appropriate.

1. Depression measured by Montgomery-Asberg Depression Rating Scales (MADRS)
2. Suicide Ideation measured by Beck Scale for Suicide Ideation (BSS)
3. Depression measured by Beck Depression Inventory (BDI)
4. Quality of Life measured by the VR-36
5. Cognitive Function as measured by a neuropsychological battery

IV. STUDY DESIGN

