			Screening/ Baseline	5	10	15	20	[25]	[30/ last]	1	2	3	4	8	12	16	20	24
86	Consent	S*																
01	Screening Form	S																
02	Randomization Form	B*																
03	Baseline	S																
04	Medical History	S																
05	Physical Exam	S							x									
06	Labs	S																
07	Structured Clinical Interview for DSM-IV-TR (SCID-I)	S																
08	Current/Past ATHF	S																
09	Lifetime Drinking History	B																
10	Clinician Administered PTSD Scale (CAPS)	B							x									x
11	Trauma History Questionnaire (THQ)	B																
12	Life Stressor Checklist-revised (LSC-R)	B																
13	Six-Item Blessed Orientation-Memory-Concentration (BOMC)	S																
14	Pregnancy Test	S ²	Every 4 weeks															
15	Medication Use	S	x	x	x	x	x	x	x	x	x	x	x	x	x	x	x	
16	Study Visit Form		x	x	x	x	x	x	x	x	x	x	x	x	x	x	x	
17	Audiometry: REMOVED																	
18	rTMS Treatment Log		x	x	x	x	x	x	x									
19	rTMS Taper Log									x	x	x						
20	Hamilton Rating Scale for Depression (HRSD) and MADRS	S ²	x	x	x	x	x	x	x				x	x	x	x	x	x
21	Beck Depression Inventory (BDI)	B	x	x	x	x	x	x	x				x	x	x	x	x	x
22	Quick Inventory of Depressive Symptomatology (QIDS-C16)	B	x	x	x	x	x	x	x				x	x	x	x	x	x
23	Columbia-Suicide Severity Rating Scale (C-SSRS)	S																
24	Columbia-Suicide Severity Rating Scale (C-SSRS) F/U		x	x	x	x	x	x	x	x	x	x	x	x	x	x	x	x
25	Beck Scale for Suicidal Ideation (BSS)	S	x	x	x	x	x	x	x	x	x	x	x	x	x	x	x	x
26	Beck Hopelessness Scale	S	x	x	x	x	x	x	x	x	x	x	x	x	x	x	x	x
27	Quality of Life (VR 36)	B							x									x

Assessment		Screening/ Baseline	Acute Treatment Phase						Follow-up Phase								
			4 - 11 weeks						24 weeks (6 months)								
			2-4 weeks		End of Session Number ¹				PRN Taper weeks		Weeks						
			5	10	15	20	[25]	[30/ last]	1	2	3	4	8	12	16	20	24
28	Neuropsychological Battery	B						x									x
29	DAST	S						x									x
30	PTSD Checklist (PCL)	B						x									x
31	MAST	S						x									x
32	STAXI-2	S	x	x	x	x	x	x	x	x	x	x	x	x	x	x	x
TLFB	Alcohol/Drug Timeline Followback (TLFB)		x	x	x	x	x	x	x	x	x	x	x	x	x	x	x
33	Urine Tox Screen/Alcohol Test	S		x		x		X		x		x	x	x		x	
34	Termination Form ³																x
35	Control Questionnaire	Before and after the 1 st treatment															x
36	Protocol Deviation	As required															
37	Adverse Events (AE) and ADE and Serious Adverse Events (SAEs) and UADE	As required															

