21. Blessed Orientation Memory Concentration Test (BOMC). The BOMC (Katzman, Brown, Fuld, Peck, Schechter, & Schimmel, 1983) is a 6-item screening measure of cognitive impairment which takes approximately 5 minutes to administer. The measure consists of 3 orientation questions, listing months backwards, a name and address memory phrase, and counting backwards from 20 to 1. This measure is fairly sensitive to milder levels of cognitive impairment.

22. Neuropsychological Battery. We propose to use a battery that is sensitive to the potential cognitive effects of rTMS. rTMS may improve cognitive function as depression is lifted, or it could have the potential for impairing function. A battery has been designed to be sensitive to such potential effects and has been used in previous studies of the effectiveness of rTMS. We propose to use measures that have been used in previous studies of rTMS as they have proven to be sensitive and it will also provide a basis for comparison of the VA patients entering this study with patients who have participated in other studies of rTMS.

The cognitive assessments will be administered at screening, at the end of the acute treatment phase and at the end of the 24 week follow-up phase. These measures are widely used in the literature and have been shown to be effective when working with severely depressed patients

Testing will include measures of Executive Function, Attention, Memory, Visuospatial Ability, Processing Speed, Psychomotor Function, and premorbid intelligence.

Executive functioning will be assessed using the **Controlled Oral Word Association (COWA) Test**, which is a test of verbal fluency. Participants are asked to produce as many words that

begin with a specific letter (F, A, or S) as they can within one minute. The participant is then asked to name as many animal names as possible within one minute (Spreen and Strauss, 2006).

Attention will be assessed using the **Stroop Color and Word test** (Golden, 1978). This measure consists of three pages: a Word page with 100 color words printed in black ink; a Color page with 100 X's printed in colored ink; and a Color-Word page that contains words from the Word page printed in colors (the word and the color do not match). Participants are asked to read as many words or name as many colors as possible in 45 seconds.

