Some secondary outcome measures, such as sustained response rate (“recovery”) and response on secondary outcome measures, can also be analyzed using logistic regression models. Other potential secondary analyses include continuous variables such as: change in suicidality, change in cognitive function and change in quality of life (QOL). The effect of rTMS on such continuous measures will be determined using random regression and similar techniques that maximize the use of available data in repeated measures designs.

Potential moderators of treatment response also will be analyzed using multivariate analysis of variance or regression techniques. In addition, exploratory analyses will be performed using signal detection techniques (Receiver Operator Characteristics or ROC) to attempt to identify novel moderators predictors of response. The following gives examples of some potential

analyses that may be carried out that use random regression techniques, which may be more sensitive to change than the logistic regression analyses.

a. Random regression approach to efficacy analyses

Random regression models will be used to test and evaluate treatment efficacy (see e.g., Gibbons et al., 1993). Such models trace the individual trajectories over time and, in effect, use available information to impute any missing data for comparable subjects. They thus compare the groups on a parameter describing the trajectory (e.g., the subject's response rate over time). This method not only minimizes loss of power and bias due to dropouts (for analytical purposes there are none), but also amplifies the reliability of measures using repeated measures per subject and thus usually increases power.

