Short-Term Efficacy (Baseline to End of Acute Treatment). This approach can be used to replicate and enhance the understanding of the main analyses. Data to be entered into the random regression analyses will include those collected at baseline and after sessions 10, 20 or possibly 30 if the patient receives treatment at that time. We will use a linear model on $\ln(t+1)$ to model the typical “fish hook” shape of the response trajectory, assuming an autoregressive covariance structure within individuals with treatment group as the independent variable. The primary outcome measure will be the slope of HRSD change. This random regression parallel of the primary analyses will provide complementary information to assess if rTMS is superior to sham rTMS. Secondary random regression analyses also will be performed on each of the other outcome measures. The effect of site will also be examined as in the primary analyses.

Longer-term efficacy (End of Treatment to End of Follow-up). Data to be entered into analyses will include those collected from weeks 4 to 24 of follow-up, and analytic techniques will parallel those described above. This will allow a comparison of loss of treatment effect from the end of the treatment to the end of follow-up, i.e. it will address questions of pattern of “recovery” and “recurrence.”

**b. Random regression approach to individual differences in response
(Moderators)**

Multiple regression analyses will be performed to determine if, as hypothesized, there will be individual differences in the efficacy of treatment depending upon specific predictors. This analysis will be done by adding the predictor variable and its interaction with treatment to the Random Regression Model used above. A significant interaction indicates a differential effect size depending on predictor status. Separate predictor of response analyses will be performed for each set of outcome data. These analyses are used to determine in whom or under what conditions improvement occurs. For example, we expect that younger age will predict a better response to rTMS than to sham rTMS. The initial measures to be used in these analyses will be severity of symptoms at baseline, type of comorbidity (PTSD, substance abuse, or both), duration of illness and prior treatment resistance.

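### The acute-phase log-time slope is extended to quality of life and cognition, which have one acute post-baseline score; a baseline-adjusted end-of-treatment comparison suits them better

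*Protocol*

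**What the plan says.** Protocol section III.B lists five secondary outcomes. The fourth is "Quality of Life measured by the VR-36" and the fifth is "Cognitive Function as measured by a neuropsychological battery".

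Section VIII.C names change in cognitive function and in quality of life among the continuous measures and states: "The effect of rTMS on such continuous measures will be determined using random regression and similar techniques that maximize the use of available data". It introduces the detailed models as examples of potential "analyses that may be carried out that use random regression techniques, which may be more sensitive to change than the logistic regression analyses".

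Section VIII.C.a, under Short-Term Efficacy, gives the acute-phase model. It begins "We will use a linear model on $\ln(t+1)$ to model the typical" shape of response, and adds an autoregressive within-patient covariance with treatment group as the predictor. The parameter of interest is the HRSD slope. The data points named are baseline and sessions 10, 20 and possibly 30. The paragraph then says: "Secondary random regression analyses also will be performed on each of the other outcome measures".

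The schedule for the two outcomes is sparser. Section VI.G.22 says "The cognitive assessments will be administered at screening, at the end of the acute treatment phase", and again at the end of follow-up. Table 2 (rows 27 and 28) shows the same pattern for the VR-36 and the battery: baseline, one acute-phase mark, week 24. By section VI.E and the first footnote to Table 2, the last acute session is 20, 25 or 30, depending on when the patient remits.

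**The concern.** A slope on log time is useful when a scale is rated repeatedly: the curve can be checked, and repeated ratings improve reliability. Section VIII.C.a justifies random regression on that ground. With a baseline and one later score, none of this applies:

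- The curve cannot be estimated or checked.
- Random slope and autocorrelation cannot be separated.
- There is no session-10 score, and session 25, which is the last session for some remitters, is not among the named time points.

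What remains is the change from baseline divided by ln(t+1) at the last session, and that divisor depends on whether and when the patient remitted. Two things could be at stake for these outcomes: precision, if the baseline value is not used as a covariate or through a common baseline mean; and interpretation, because the reported quantity mixes the size of the change with the stopping time.

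**Working it through.** **Inputs from the protocol.** 180 per arm and planned remission of 6% sham v 16% rTMS (VIII.A); last acute score after session 20, 25 or 30 (VI.E, Table 2). The protocol gives no figure for the random regression. As a check on the inputs, power for 6% v 16% with 180 per arm is 82.0% with continuity correction and 86.1% without, against the stated 81%. Two-sided 0.05 is assumed here, since 0.05 appears only in the monitoring-boundary example.

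**Assumptions not in the protocol.** Outcome SD 1; baseline-to-end correlation r = 0.5, range 0.3 to 0.8; true effect 0.30 SD; correlation of the outcome residual with remission 0.3 to 0.9; 50% to 100% of remitters stopping at session 20.

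**1. Rescaling of one patient's change.** The unit of t is not stated.
- Sessions: ln(31)/ln(21) = 3.434/3.045 = 1.128, so the same change gives a 12.8% steeper slope at session 20 than at session 30.
- Weeks, at one block per week: ln(7)/ln(5) = 1.946/1.609 = 1.209, so 20.9% steeper.

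These compare two patients' divisors. They are not effects on the treatment comparison.

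**2. Precision with separate intercepts by arm.** The test then behaves as a change score.
- Change score: variance of the difference = 2 × 2(1 − r)/n.
- ANCOVA: variance of the difference = 2 × (1 − r²)/n.
- Ratio = 2(1 − r)/(1 − r²) = 2/(1 + r).

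| r | variance ratio | SE ratio |
|---|---|---|
| 0.3 | 1.538 | 1.240 |
| 0.5 | 1.333 | 1.155 |
| 0.7 | 1.176 | 1.085 |
| 0.8 | 1.111 | 1.054 |

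At r = 0.5 and n = 180, the SE is √(2 × 1.0/180) = 0.105 for change and √(2 × 0.75/180) = 0.091 for ANCOVA. A variance ratio of 1.333 corresponds to 180/1.333 = 135 patients per arm. In simulation the slope model with separate intercepts had SE 0.106 to 0.107 and power of about 79% to 82% for a 0.30 SD effect, against about 91% for ANCOVA.

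**3. Precision with a common baseline mean.** The same slope model had SE 0.092 to 0.093 and power of about 91%. Against ANCOVA, the SE cost is about 1%.

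**4. Bias at 6% v 16% remission, true effect 0.30.**
- Model-based fit with autoregressive covariance: 0.296 to 0.306, about −1% to +2%. A variant with last scores at 4, 5 and 11 calendar weeks gave 0.292 with separate intercepts (0.292/0.300 = 0.973, an understatement) and 0.300 with a common baseline.
- Unweighted average of per-patient slopes: +4.2% (sessions) and +6.8% (weeks) when half the remitters stop at session 20 and a quarter at 25. It reached +17.1% only with t in weeks, every remitter stopping at session 20 and a residual correlation of 0.9.

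The two differ because a pooled slope of the form Σ(g × change)/Σg², with g = ln(t+1), gives early stoppers less weight and so offsets their steeper individual slopes. In the two base cases above it gave 0.302 and 0.303.

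**5. No true effect.** Bias in the model-based fit was at most 0.012 SD, and rejection stayed at about 4% to 5%.

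**The case against.** Four points can be made for the protocol.

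First, section VIII.C offers these models as examples and allows similar techniques, and section VIII.E calls the whole a brief outline. The log-time curve and its time points are described alongside the HRSD slope. This stands, and it limits the weight of the point. It does not remove it, because the text also says these analyses will be performed on each other outcome measure and specifies no other acute-phase model for them.

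Second, the precision loss is conditional. A reader might infer that the stated method must lose precision against ANCOVA. The protocol does not say whether baseline means are separate by arm or held common. Separate intercepts are the usual reading of a group plus group-by-time model, but a common baseline is not ruled out and loses almost nothing.

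Third, a reader might infer that the slope overstates the benefit because rTMS should produce more early remitters. The documents do not support this. At the planned rates the model described is nearly unbiased, and its small error changes sign. The 3% to 7% figures need averaged per-patient slopes, which the protocol does not describe. A clear overstatement in the model-based fit (0.33 to 0.34 for 0.30) needed remission of 20% v 40%.

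Fourth, under a rate-of-response estimand, the same gain reached sooner should count for more. That is a coherent position. But with one score the speed of change is not observed for these outcomes; only the session at which HRSD remission ended treatment is.

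**Conclusion.** The mismatch is real and the point is modest. For the VR-36 and the neuropsychological battery, the acute-phase slope on ln(t+1) cannot do what it is meant to do and reduces to a change score rescaled by stopping time.

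If the arms have separate intercepts, the standard error is about 15% larger than with baseline-adjusted ANCOVA at r = 0.5, and between about 5% and 24% larger for r from 0.8 down to 0.3. If the baseline mean is common to the arms, the loss is about 1%. The correlations are assumed; the protocol gives none. Bias from the rescaling is small at 6% v 16% remission, and type I error is not affected. The primary analysis and the scales rated at every block are untouched.

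**What to change.** In section VIII.C.a, keep the ln(t+1) slope model for scales rated at every treatment block. For outcomes with one acute post-baseline score (the VR-36 and the neuropsychological battery, and also the CAPS and PCL if they are analysed this way), state that the end-of-acute score is compared between arms, whether taken after session 20, 25 or 30. Use ANCOVA with the baseline value and the primary-model covariates (PTSD diagnosis, history of substance abuse, site), or a two-visit model with a common baseline mean, which also keeps patients who lack the second score.

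The cost is one or two sentences and no new data, and the wording of VIII.C already leaves room for it. The downside is that these outcomes are reported as an end-of-treatment difference and not as a slope.

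### The follow-up random regression claims to measure loss of effect from the end of treatment, but its data start at follow-up week 4

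*Protocol*

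**What the plan says.** Section VIII.C.a of the Protocol describes two random regression analyses.

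- **Short-term, baseline to end of acute treatment.** The starting point is named: "Data to be entered into the random regression analyses will include those collected at baseline and after sessions 10, 20 or possibly 30". The model is linear in ln(t+1), with an autoregressive covariance within patients, and its outcome is the slope of HRSD change. The paragraph adds: "Secondary random regression analyses also will be performed on each of the other outcome measures".
- **Longer-term, end of treatment to end of follow-up.** The data rule is "Data to be entered into analyses will include those collected from weeks 4 to 24 of follow-up", the techniques are to follow those of the short-term analysis, and the purpose is given as "a comparison of loss of treatment effect from the end of the treatment to the end of follow-up".

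Table 2 (Section VI.G) schedules HRSD and MADRS after every five-session block up to and including the last acute session, not in taper weeks 1 to 3, and then at follow-up weeks 4, 8, 12, 16, 20 and 24. VR-36, the neuropsychological battery, CAPS, PCL, MAST and DAST are scheduled only at screening or baseline, at the end of acute treatment and at week 24. Section VI.G.22 confirms this for cognition: "cognitive assessments will be administered at screening, at the end of the acute treatment phase and at the end of the 24 week follow-up".

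Section VI.E places the three-week taper inside the follow-up phase and gives it only to patients who remit.

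**The concern.** Loss of effect measured from the end of treatment needs the score at the end of treatment. The data rule leaves it out, although it is collected. A patient who worsens before week 4 and then stays level contributes a flat line, which the model reads as no loss.

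The omitted interval is not a neutral one. It holds the taper, which depends on remission. At the protocol's design rates (Section VIII.A: 16% active, 6% sham, 180 per group) that means about 0.16 × 180 = 29 active and 0.06 × 180 = 11 sham patients. Section VI.K also allows psychiatric medication to be adjusted once the acute phase is over.

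A second issue arises if the slope model is carried into follow-up for outcomes other than the depression and suicidality scales. Several of these have a single visit between weeks 4 and 24.

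At stake is the interpretation of a secondary durability analysis. Durability is the first secondary objective; quality of life, cognition, PTSD and substance abuse appear in the third.

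**Working it through.** The plan gives no figure for this analysis, so there is none to reproduce. The check has three parts.

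**1. Purpose against data.** The purpose runs from end of treatment to week 24 and the data run from week 4 to week 24. The short-term paragraph lists its own starting point, so the follow-up list can fairly be read as the data specification. The missing point is available from the last acute session (Table 2).

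**2. How much slope information the omitted point carries.** For a time variable x, slope information with independent errors is proportional to SSx = Σ(x − mean x)². Compare t = 4, 8, 12, 16, 20, 24 weeks of follow-up with the same visits plus the end-of-acute point. The protocol does not say in what unit, or from what origin, t is counted in follow-up, so several readings are shown.

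| Time variable | SSx, weeks 4–24 | SSx with end-of-acute point | Share kept |
|---|---|---|---|
| ln(t+1), weeks from end of treatment | 1.777 | 7.474 | 24% |
| ln(t+1), weeks from treatment start, 4-week acute phase | 0.947 | 2.311 | 41% |
| ln(t+1), weeks from treatment start, 11-week acute phase | 0.457 | 0.922 | 50% |
| Linear t | 280 | 448 | 62.5% |

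The 4 and 11 weeks are the protocol's limits for the acute phase (Section VI.D). On the first row's scale, the part of the time range before week 4 is ln 5 / ln 25 = 1.609 / 3.219 = 50%. On linear time it is 4/24 = 17%. Counting days from end of treatment would make it ln 29 / ln 169 = 66%.

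With an autoregressive covariance, V(i,j) = ρ^(|ti − tj|/4), and the slope variance is the slope element of (X′V⁻¹X)⁻¹. On the first row's scale, the ratio of the weeks 4–24 variance to the variance with the end-of-acute point is:

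| ρ at a 4-week lag (assumed) | Variance ratio | SE ratio |
|---|---|---|
| 0.30 | 4.36 | 2.09 |
| 0.50 | 4.50 | 2.12 |
| 0.70 | 4.68 | 2.16 |
| 0.85 | 4.86 | 2.20 |

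These ratios belong to that scale only. They also ignore between-patient variation in slopes, which would shrink the gain from adding a point.

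**3. Visits inside weeks 4–24, counted from Table 2.**

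| Outcome | Weeks 4–24 | With end-of-acute value |
|---|---|---|
| HRSD, MADRS, BDI | 6 | 7 |
| VR-36, neuropsychological battery, CAPS, PCL, MAST, DAST | 1 | 2 |

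One value per patient supports neither a within-patient slope nor an autoregressive correlation. Two values support a change, but not separate estimation of a random slope and an autoregressive parameter. Adding the starting point therefore repairs the HRSD analysis but is not enough for the sparse scales.

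**The case against.** The strongest case on the other side has five parts.

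- **Status.** Section VIII.C introduces these models as examples of analyses that might be done, and Section VIII.E calls the listing an outline. The wording of the data rule is also not strictly exclusive. This stands and limits the weight of the point. It does not remove the mismatch, because the protocol itself states both the window and the purpose.
- **Durability has another route.** A reader might infer that the trial cannot test durability. The documents do not support that. Sustained remission can be analysed by logistic regression under Section VIII.C, independently of this model. The follow-up model also still estimates a valid slope from week 4 and an arm difference at week 4. What it does not estimate is the change from end of treatment to week 4.
- **Sparse scales.** A reader might infer that quality of life, cognition and PTSD outcomes cannot be analysed at all. That goes too far. The sentence on the other outcome measures sits in the short-term paragraph, and its extension to follow-up is an inference from the statement that the techniques run parallel. Section VIII.C separately allows random regression or similar repeated-measures techniques for cognition and quality of life, without confining them to weeks 4–24. Of the five secondary outcomes in Section III.B, only VR-36 and cognition are sparse; MADRS, BDI and BSS are measured throughout follow-up.
- **Time scale.** The logarithmic scale was chosen for the shape of the acute response, and no origin is given for follow-up. This stands: 24% is one reading, not a property of the plan.
- **Selection.** Acute treatment ends once HRSD is 10 or less, so a remitter's last acute score is selected for being low, and some later rise may be regression to the mean, unequally by arm if remission rates differ. This is a sound caution about reading the slope and a good reason to keep the weeks 4–24 fit alongside. It does not justify dropping the point from which the analysis says it measures.

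**Conclusion.** The point holds within limits. As written, the longer-term random regression does not measure change between the end-of-acute score and week 4, although its stated purpose starts at the end of treatment. That finding needs no numerical assumption.

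The loss of precision does depend on assumptions: the weeks 4–24 window keeps between about 24% and 62.5% of the time sum of squares across the week-based readings tabulated, and the protocol does not say which applies.

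The single-observation problem is conditional. It arises only if the weeks 4–24 slope model is applied to the three-occasion scales, and the protocol leaves room to analyse quality of life and cognition differently.

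This is a secondary analysis worth correcting. It does not threaten the primary analysis or the logistic analysis of sustained remission.

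**What to change.** In the longer-term paragraph of Section VIII.C.a:

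1. Enter the end-of-acute-treatment value as the starting point, t = 0, and state the unit and form of time for follow-up.
2. Keep the fit restricted to weeks 4–24 as a sensitivity analysis, noting that remitters' last acute score is selected for being 10 or less.
3. For VR-36, the neuropsychological battery, CAPS, PCL, MAST and DAST, replace a weeks 4–24 slope by a repeated-measures model of the end-of-acute and week-24 values, adjusted for the baseline value, with treatment-by-visit terms.

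The cost is analysis wording only. Every value needed is already in Table 2, and no visit, assessment or sample size changes.
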